- (3) Risks of Collecting Personal Information: One potential risk is breach of confidentiality related to the collection of sensitive information, but this will be minimized by following standardized procedures to protect all such information.

Protection Against Risk:

Risk of EEG: We will monitor the children during the studies and can adjust or remove the EEG caps if there is any discomfort.

Risk of TMS: We protect against the risk of seizure by having a pediatric epileptologist ([name]) in the room during all TMS procedures and actively monitoring the EEG during stimulation so that stimulation can be stopped if there are any concerns. Furthermore, we use only single pulse stimulation and low-frequency repetitive stimulation (<1Hz), both of which have been well studied and are quite safe. [name] will be present for all TMS sessions. She has extensive experience performing TMS in children and clinical expertise in the management of seizures in children. Furthermore, all TMS will be done at Stanford University in close proximity to Lucile Packard Children's Hospital. Any persons assisting with the TMS will undergo TMS safety training and seizure training. All children wear noise-cancelling

headphones to protect their ears from the TMS click. Scalp burns are prevented using cooled-coils. We speak with children throughout the TMS session so will actively monitor them for any other discomfort. If there is minor discomfort due to the TMS, the study will be paused and potentially halted.

Risk of Loss of Privacy: To maintain confidentiality, we will restrict access of private health information exclusively to the PI, necessary personnel of the Data Safety Monitoring Board and research staff. We will de-identify all data obtained from subjects. We will store all data on a PGP encrypted server within the School of Medicine at Stanford University. All hard copies of data, including medical records and copies of informed consent, will be maintained in a locked file cabinet in the lab. All members of the research team will undergo HIPPA training.

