Additional Protections for Children: The study is recruiting children as BECTS is a pediatric condition not present in adults; there are also no good animal models of this condition. The study procedures will be reviewed with the children in language they can understand before the protocol begins and children will be told they can stop the study at any time. Parents of children participating will also be informed that they are free to choose not to participate and may withdraw at any time. We will obtain assent from children who are of an appropriate age (typically >8yo of age). We will frequently check-in with children throughout the study to ensure that they are comfortable with continuing the procedures.

Potential Benefits: IEDs lead to cognitive problems in some children. Participants may benefit by having a reduction in IEDs at least temporarily. Additionally, we will learn more about the pathophysiology of BECTS, which may improve treatment in the future.

OBJECTIVES & ENDPOINTS

OBJECTIVES	ENDPOINTS	JUSTIFICATION FOR ENDPOINTS	RATIONALE
To evaluate if rTMS reduces the frequency of IEDs in children with BECTS.	Change in IEDs/minute induced by active rTMS vs. change induced by sham rTMS. Change will be calculated by comparing IED count in the 20 minutes after rTMS with IED count in the 20 minutes before rTMS.	This will assess if rTMS reduces IED frequency when compared to a sham control.	There is evidence that rTMS reduces cortical excitability and hence may reduce generation of IEDs.

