To evaluate if rTMS reduces connectivity between the motor and language regions in children with BECTS.	Change in weighted phase lag index (wPLI) (an EEG-based connectivity measure) between the stimulated motor cortex and the left inferior frontal gyrus induced by active rTMS vs. sham rTMS. Change will be calculated by comparing wPLI in the 20 minutes after rTMS vs. the 20 minutes before rTMS. We will collect 2 types of EEG data before and after the active/sham rTMS: (a) spTMS-EEG, and (b) resting-state EEG; and Connectivity will be calculated for each of these data types separately.	This endpoint will help us determine the downstream effect of rTMS on other brain networks.	Epilepsy is a network disorder and fMRI studies suggest that IEDs from the motor cortex increase connectivity between the motor cortex and inferior frontal gyrus. Therefore, inhibition of IEDs and increased inhibition of the motor cortex may decrease connectivity between the motor cortex and inferior frontal gyrus.

STUDY DESIGN

Overview: Children with BECTS will undergo both active rTMS and sham rTMS to the epileptogenic motor cortex. We will compare the impact of active vs. sham rTMS on: (a) IED frequency; and (b) motor-to-language connectivity. We hypothesize that active rTMS induce a greater decrease in: (a) IED frequency and (b) motor-to-language cortex connectivity than sham rTMS.

Study Stage: Stage 0

Study Design: Sham-controlled cross-over study in which all participants will receive both active and sham rTMS, with randomization of order of intervention. We will have repeated-measures data as subjects will undergo both sham and real rTMS on different days. The potential missing data issue will be evaluated thoroughly prior to the analysis. Multiple imputation will be applied if needed.

Assignment Methods: Not applicable, subjects will undergo both active and sham rTMS.

Study Arms: All subjects will participate in each arm, and arm order will be randomized on a per-subject basis. Participation in each arm will take approximately 4 hours (including set-up of equipment and data recording). Arms will be separated by at least 1 week.

Arm 1 (active rTMS): 1000 pulses of rTMS administered via an active TMS coil at 1Hz to the motor cortex. EEG and spTMS-EEG data will be recorded during the 20 minutes prior to and following the rTMS.

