The order of conditions (active vs. sham rTMS) will be randomized on a per-subject basis. A random number generator will be used to create a random list using numbers 1-40. Subjects whose recruitment lines up with an even number will receive active rTMS in the first session and sham rTMS in the second session and vice versa for odd numbers. Participants will be blind to the condition order. The sham rTMS will be administered using the same parameters and same stimulation site as the active stimulation. The intensity of the sham coil is such that it is expected to create a scalp sensation without inducing an intracranial current. It is possible that some subjects will recognize a difference between the 2 sessions, and we will ask them after each session to assess if it was active vs. sham rTMS. If subjects can consistently identify a difference, than we will report that blinding was not successful in our final analyses.

Researchers will not be blinded during the session, but the data will be coded prior to analysis and the person performing the analysis will be blinded to the session type.

STUDY PROCEDURES

Screening: For subjects referred by their physician, the study team will confirm the diagnosis of BECTS with the referring provider. Parents of participants will then be called by a member of the research team and screened on the inclusion and exclusion criteria. If the parents primarily speak a different language than English, the screening will be conducted with the help of an interpreter or by a study team member fluent in that language.

For subjects who self-refer to the study, the study team will review the inclusion and exclusion criteria with the family. Subjects who screen-in and consent to the study will be asked to bring a physician's note stating their diagnosis and prior EEG findings.

Screening will be done within 2 months of participation. If this time window is delayed, the inclusion/exclusion criteria will be reviewed on the day of the first intervention to ensure the subject is still eligible.

Informed Consent & Assent: Since informed consent is required from both parents and/or legal guardians if they are reasonably available (i.e. not deceased, imprisoned, whereabouts unknown or not involved in the care of the child), informed consent will be first obtained over the telephone with the help of an interpreter if necessary. Assent will be obtained from the participating child on the day of the first rTMS session.

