Impact of Repetitive Transcranial Magnetic Stimulation (TMS) on Spike Frequency and Brain Connectivity in Children with Benign Epilepsy with Centrotemporal Spike (BECTS)

Statistical Analysis Plan

NCT04325282

July 9, 2025

We used the Wilcoxon signed-rank test, a non-parametric test appropriate for data that is not normally distributed, to assess changes in IED frequency and brain connectivity (as measured by the weighted Phase Lag Index [wPLI] between six regions of interest, yielding 15 unique region-to-region pairs). First, we measured change *within* each session by comparing post-rTMS to pre rTMS recordings (post vs. pre active rTMS IED & connectivity values; post vs. pre sham rTMS IED & connectivity values). Second, we compared the changes induced by active vs. sham rTMS to one another.

Given the multiple ROIs investigated, we adjusted significance thresholds using principal component analysis, which accounts for the effective number of independent tests. This method is suitable when data in each comparison are not completely independent, as is the case with EEG where signal represents summated activity from multiple regions. In contrast, correction methods that assume complete independence (e.g., Bonferroni) may set overly conservative thresholds that obscure meaningful findings.

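### Analyst masking is specified for session type only, so the SAP's within-session post-versus-pre tests are open to expectation bias if marking involves judgement

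*Protocol*

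**What the plan says.** Protocol, Randomization & Blinding, states that "Researchers will not be blinded during the session". The safeguard for the outcome is then that "the data will be coded prior to analysis and the person performing the analysis will be blinded to the session type". The same section says of the sham: "The intensity of the sham coil is such that it is expected to create a scalp sensation without inducing an intracranial current".

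Protocol, Objectives & Endpoints, defines the IED endpoint as a between-session contrast, "Change in IEDs/minute induced by active rTMS vs. change induced by sham rTMS", built from a within-session one: "Change will be calculated by comparing IED count in the 20 minutes after rTMS with IED count in the 20 minutes before rTMS". The connectivity (wPLI) endpoint has the same structure. Protocol, Study Design, says for each arm that "EEG and spTMS-EEG data will be recorded during the 20 minutes prior to and following the rTMS". The hypothesis in that section is directional: a larger fall under active than under sham.

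The SAP tests both levels. It first assesses change within "each session by comparing post-rTMS to pre rTMS recordings", separately for active and sham, and then compares the two changes. It does not mention blinding.

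Protocol, Risks/Benefits (Protection Against Risk), describes "actively monitoring the EEG during stimulation" as a safety measure.

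The documents do not say who marks IEDs, whether marking is by eye or by software, whether that person is the blinded analyst, whether the coding hides the pre/post label, or whether the EEG from the stimulation period is saved in the coded file.

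**The concern.** Masking to session type hides active versus sham. It does not by itself hide before versus after, and before versus after is exactly what the SAP's first set of tests compares. If a person marks IEDs or rejects epochs knowing which window followed stimulation, and expects stimulation to reduce discharges, borderline events can be treated differently in the two windows. A test of post against pre would then pick up the reader's expectation as though it were an effect.

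There is a second, more conditional route. The sham coil is not meant to induce an intracranial current. If the stimulation stretch stays in the file and looks different under the two coils, the reader might work out the session type, and the active-versus-sham comparison would be exposed too.

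At stake are any statements that IEDs fell after active rTMS (or after sham) on the strength of the within-session tests and, under the second route only, the protocol's own endpoints.

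**Working it through.** The documents give no effect size, SD, alpha or power tied to this point, so there is no stated figure to reproduce. What follows is illustrative.

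**Inputs**
- From the documents: 36 to 40 children (Protocol, Recruitment & Retention); 20-minute windows; Wilcoxon signed-rank tests (SAP).
- Assumed: undercount b of IEDs in post windows of 5%, 10% or 20%; SD of the log post/pre ratio of 0.5 or 0.8; two-sided 5% level; no true effect.

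**1. Within-session test, normal approximation, n = 36**

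Shift: z = −ln(1 − b) × √36 / SD. Rejection probability: P(Z > 1.96 − z) + P(Z < −1.96 − z).

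| b | −ln(1 − b) | z, SD 0.5 | Rejects | z, SD 0.8 | Rejects |
|---|---|---|---|---|---|
| 5% | 0.0513 | 0.62 | 9% | 0.38 | 7% |
| 10% | 0.1054 | 1.26 | 24% | 0.79 | 12% |
| 20% | 0.2231 | 2.68 | 76% | 1.67 | 39% |

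**2. Active versus sham, reader blind to session type**

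Let a child's true rate be λ and the true proportional reduction under active be e, with none under sham. A reader who undercounts by b in both post windows records expected changes of:
- active: λ[(1 − e)(1 − b) − 1]
- sham: λ[(1 − b) − 1]
- difference: −eλ(1 − b)

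With e = 0 the difference is zero whatever b is. With e > 0 it shrinks by the factor (1 − b). For λ = 5 per minute and e = 30%, it is −1.50, −1.35 and −1.20 per minute at b = 0, 10% and 20%.

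**3. Simulation with the SAP's test**

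This used the Wilcoxon signed-rank test, 1,500 runs per setting, and n = 36 and 40. Further assumptions: mean 5 IEDs per minute, gamma spread between children (shape 1), 30% coefficient of variation between recordings, Poisson counts over 20 minutes. At a true 5% level the simulation standard error is √(0.05 × 0.95 / 1500) ≈ 0.006.

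Type I error (ranges cover n = 36 and 40 and, for the within-session test, both sessions):

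| b | Within-session, session type masked | Active vs sham, session type masked | Active vs sham, 75% of sessions recognised | Active vs sham, 100% recognised |
|---|---|---|---|---|
| 5% | 0.08–0.09 | 0.04–0.05 | 0.06–0.07 | 0.06–0.07 |
| 10% | 0.22–0.25 | 0.05–0.06 | 0.06–0.07 | 0.12–0.14 |
| 20% | 0.67–0.73 | 0.05 | 0.12–0.13 | 0.36–0.40 |

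The last two columns place the undercount only in the session the reader believes is active. With b = 0, all tests sit near 0.05 (0.04–0.06).

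With a true 30% reduction, n = 36 and session type masked, active-versus-sham power is 0.70, 0.65 and 0.57 at b = 0, 10% and 20%. That is the dilution in step 2.

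The within-session column agrees in order of size with the SD 0.5 figures in step 1, although the models differ.

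**The case against.** The strongest reply is that the documents are silent, not wrong. Coding might already hide the window labels, and marking might be automated. No human reader is described, and wPLI is a computed index. This stands. It would be too strong to infer that the analyst is known to see pre/post labels, or that IEDs are known to be marked by eye. What can be said is that masking of time is not specified. Nor is there a basis for saying which way epoch rejection would push wPLI, so the figures above concern IED counts only.

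A second reply is that the protocol's endpoints are between-session differences, and a shared undercount cancels there. This also stands. A reader might infer that knowing pre from post biases the active-versus-sham result towards active. Step 2 of the working shows that it does not while session masking holds.

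A third reply concerns the stimulation record. A reader might infer that the coded file reveals the condition. The documents describe live monitoring during stimulation but do not say that this stretch is saved or passed to the analyst. They do not describe the EEG artefact of either coil, and a lack of intracranial current does not establish that the scalp record looks different. This route is a possibility worth closing, not a documented breach.

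Finally, the SAP is dated July 2025 and written in the past tense, so reading may be complete. That changes the form of the remedy but does not remove the point, because the within-session tests will still be reported.

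**Conclusion.** The point holds in limited form. Masking is specified for session type only, while the SAP tests post against pre within each session. If marking involves judgement, those within-session IED tests can reject far above 5% with no true effect: about 9%, 24% and 76% for undercounts of 5%, 10% and 20% at SD 0.5, and about 7%, 12% and 39% at SD 0.8. Both the undercount and the SD are assumptions, and a fully automated detector would largely remove the concern.

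The active-versus-sham endpoints keep their type I error while session masking holds and lose only some power. Inflation there needs the reader to recognise the condition, which nothing in the documents shows to be happening. The change is worth making because it is cheap and closes both routes.

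**What to change.** Amend Protocol, Randomization & Blinding, and repeat the rule in the SAP:

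- State who marks IEDs and rejects epochs, whether by eye or by software, and whether that person is the blinded analyst.
- Before marking and rejection, export each recording as separate pre and post clips without the rTMS period.
- Strip date, session number and pre/post label, and assign a new code. The study number should not serve as that code, because under Study Procedures (Coding of Subjects & Randomization) it is also what is matched to the list that sets session order.
- Read the clips in random order. An existing team member who does not read them holds the key until counts and rejections are locked.

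The same single-pulse and resting blocks are run before and after rTMS, so the clips should be similar enough in structure for shuffling to work.

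If reading is already complete, either re-read the stored recordings this way, or report the within-session tests as not blinded to time and rest conclusions on active versus sham.

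Cost: a short export script and a few sentences of text, with no added procedure for the children. The reader loses within-session context for ambiguous discharges. A re-read would cover about 144 to 160 windows (36 to 40 children × 2 sessions × 2 windows).

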Impact of Repetitive Transcranial Magnetic Stimulation (TMS) on Spike Frequency and Brain Connectivity in Children with Benign Epilepsy with Centrotemporal Spike (BECTS)

Statistical Analysis Plan

NCT04325282

July 9, 2025

We used the Wilcoxon signed-rank test, a non-parametric test appropriate for data that is not normally distributed, to assess changes in IED frequency and brain connectivity (as measured by the weighted Phase Lag Index [wPLI] between six regions of interest, yielding 15 unique region-to-region pairs). First, we measured change *within* each session by comparing post-rTMS to pre rTMS recordings (post vs. pre active rTMS IED & connectivity values; post vs. pre sham rTMS IED & connectivity values). Second, we compared the changes induced by active vs. sham rTMS to one another.

Given the multiple ROIs investigated, we adjusted significance thresholds using principal component analysis, which accounts for the effective number of independent tests. This method is suitable when data in each comparison are not completely independent, as is the case with EEG where signal represents summated activity from multiple regions. In contrast, correction methods that assume complete independence (e.g., Bonferroni) may set overly conservative thresholds that obscure meaningful findings.

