iii. Interictal epileptiform discharges (IEDs) may interrupt normal language development. Substantial evidence indicates that IEDs cause transient changes in perception, processing, and reactivity.[26] Disorders like Landau-Kleffner Syndrome – in which patients experience a sudden language regression accompanied by constant IEDs throughout sleep but few EEG abnormalities during the day – suggest that frequent nocturnal IEDs may be sufficient to disrupt cognition.[27] In BECTS, the effects of IEDs have largely been inferred from studies correlating diurnal[14] and nocturnal[15,16] IED burden with degree and type of cognitive dysfunction, though not all studies have found a correlation.[4] Location of IEDs likely matters; of the 60% of BECTS patients with unilateral discharges, those with left-lateralized IEDs have greater language dysfunction while those with right-lateralized IEDs have greater spatial dysfunction.[8,17,18]

iv. Brain connectivity is altered in BECTS, potentially due to IEDs. fMRI studies suggest that in BECTS, the epileptogenic motor cortices have abnormal structural and functional connections with various regions.[10–13,28–33] Broader resting state networks[33–35] are also altered. A series of studies[9–11,36] found that BECTS patients have *decreased* connectivity between the motor cortex and language regions, but these studies did not account for the effect of IEDs. In contrast, Xiao et al.[33] found that connectivity between the motor cortex and inferior frontal gyrus increases after IEDs, and that greater connectivity correlates with worse language function. This literature suggests that the immediate impact of IEDs on connectivity may differ from persistent connectivity changes that develop with chronic IED exposure. This highlights a need to investigate both types of connectivity. Furthermore, connectivity differences may be especially prominent during language tasks compared to when at rest.[24]

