Active rTMS: The active intervention is 1Hz rTMS applied with an active coil to the motor cortex. Low frequency (1Hz or slower) rTMS can induce changes in brain excitability lasting minutes to hours [43,44] and has been shown to reduce IED frequency in patients with refractory focal epilepsy.[21,45] Focal changes induced by rTMS have downstream effects on brain regions connected to the stimulated motor cortex. Theoretically, 1Hz active rTMS will reduce cortical excitability of the epileptogenic motor cortex, thus reducing IED frequency. Furthermore, it will alter connectivity between the epileptogenic motor cortex and other connected cortices. Thus, we are measuring IED frequency and EEG-based connectivity.

Sham rTMS: The sham control is 1Hz rTMS administered with a sham coil, which will help account for the impact of other components of the experimental session (i.e. fear, boredom, variable attention).

rTMS Administration: The rTMS (sham and active) will be administered by a study team including [name] and a research assistant over the course of 2 sessions separated from one another by at least a week. This will occur in a room dedicated to the TMS session. The rTMS will be administered as 2 blocks of 500 pulses applied at 1Hz to the motor cortex. A break of 2-3 minutes between blocks is acceptable if needed to allow for maximum participation. The sham rTMS will be administered using the same parameters and same stimulation site, but the intensity of the sham coil is such that it is not expected to induce an intracranial current.

RANDOMIZATION & BLINDING:

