First rTMS Session: BECTS subjects will wear a 64-channel TMS-compatible high-density EEG cap while watching a video and listening to white noise. We will use neuro-navigation software to co-register the head and electrode positions to a representative pediatric brain or to the subject's MRI if one is clinically available. At the beginning of the session, we will monitor the EEG recording to determine if IEDs are unilateral or bilateral. We will then measure the resting motor threshold (rMT) for the hemisphere with the higher IED burden or the left hemisphere if IEDs are bilateral. The rMT will be established in the standard way.⁵⁵ We will apply 150 single pulses of TMS (spTMS) at 90% rMT in 2 blocks, with additional resting-state EEG (without spTMS) data gathered between these blocks. The patient will then receive either 1000 pulses of 1Hz rTMS at 90% rMT or 1000 pulses of sham 1Hz rTMS to the motor cortex, depending on the prior randomization. After the rTMS, we will repeat the blocks of spTMS interspersed with resting-state EEG.

Second rTMS Session: The second session will occur at least one week after the first session, but ideally will be done within 2-4 weeks of the first. In the second session, the procedures will be repeated as above except the other intervention will be administered. Of note, occasionally IED-predominance shifts hemispheres between EEGs. We will stimulate the same side as received rTMS during the first session unless >80% of IEDs are emerging from the contralateral hemisphere. If this occurs, we will stimulate the contralateral hemisphere and request that the subject come in for a third “tie-breaker” session.

REFERENCES

- [3] Wirrell EC. Benign epilepsy of childhood with centrotemporal spikes. *Epilepsia* 1998;39 Suppl 4:S32-41.

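### The protocol's single connectivity endpoint (stimulated motor cortex to left inferior frontal gyrus) has no identified test in the SAP, which tests 15 equal-status pairs among six unnamed regions

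*SAP*

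**What the plan says.** **Protocol (30 June 2020), Objectives & Endpoints.** The connectivity endpoint is the change in wPLI "between the stimulated motor cortex and the left inferior frontal gyrus induced by active rTMS vs. sham rTMS". It is to be derived from spTMS-EEG and from resting-state EEG: "Connectivity will be calculated for each of these data types separately". The justification column is wider, referring to "the downstream effect of rTMS on other brain networks", but the endpoint column names one pair only.

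**Protocol, First rTMS Session.** The motor threshold, and with it the side treated, is determined "for the hemisphere with the higher IED burden or the left hemisphere if IEDs are bilateral".

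**Protocol, Second rTMS Session.** "We will stimulate the same side as received rTMS during the first session unless >80% of IEDs are emerging from the contralateral hemisphere". When the side does switch, a third session is requested as a tie-breaker.

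**SAP (9 July 2025), first paragraph.** wPLI is assessed "between six regions of interest, yielding 15 unique region-to-region pairs", using Wilcoxon signed-rank tests: post versus pre within active, post versus pre within sham, and then the active change against the sham change.

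**SAP, second paragraph.** Significance thresholds are adjusted by a principal-component estimate of the effective number of independent tests. No alpha, effective number, threshold or family is given.

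**The concern.** A reader who wants the answer to the protocol's second objective needs to know which result supplies it. The protocol says which pair that is. The SAP does not carry it forward: it mentions neither the motor cortex nor the inferior frontal gyrus, and treats all 15 pairs alike. Following the SAP alone, an analyst could not say which of the 15 results is the endpoint, or whether the endpoint pair is among them.

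Side coding makes this more than a labelling matter. The protocol pair joins a motor region that depends on where the child was stimulated to a frontal region that is always on the left. Unless the analysis codes the two ends differently, the endpoint is not any one of the 15 pairs across the whole sample.

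At stake is whether the connectivity conclusion rests on the endpoint set in 2020 or on whichever of 15 pairs comes to the fore. The IED-frequency endpoint involves no region pairs and is unaffected.

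**Working it through.** 1. **The SAP's count.** Six regions give 6 × 5 / 2 = 15 unique pairs, as stated.

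2. **The two documents side by side.**

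| Item | Protocol | SAP |
|---|---|---|
| Pairs | 1, named | 15, none named |
| Regions | Stimulated motor cortex; left inferior frontal gyrus | Six, not named |
| Contrast | Active change vs sham change | The same, plus two within-session contrasts |
| Data types | 2, separately | Not mentioned |
| Stimulated side | Varies by child; may switch | Not mentioned |
| Priority | The stated endpoint | None |

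3. **Mapping the protocol pair to region labels.** For a left-stimulated child it is left motor to left frontal, within one hemisphere. For a right-stimulated child it is right motor to left frontal, across hemispheres.
   - With fixed left/right labels, these are two different pairs.
   - If all regions are relabelled as stimulated side and opposite side, the endpoint is same-side motor-to-frontal for left-stimulated children and stimulated-side motor to opposite-side frontal for right-stimulated children. Again these are two pairs.
   - Only coding the motor region by the side stimulated, with the frontal region held on the left, gives the protocol's pair for everyone.

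4. **How many children this touches.** Inputs: the protocol's Literature Review iii, "of the 60% of BECTS patients with unilateral discharges", and planned recruitment of 36 to 40. Assumptions: that literature share applies here, all bilateral cases are stimulated on the left, and the right-sided share of unilateral cases is 50%, varied from 30% to 70%. Right-stimulated children = 0.60 × share × n.
   - Share 50%: 0.60 × 0.5 × 36 = 10.8; 0.60 × 0.5 × 40 = 12.
   - Share 30%: 0.60 × 0.3 × 36 = 6.5.
   - Share 70%: 0.60 × 0.7 × 36 = 15.1.

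5. **Children whose side switches.** With two sessions on opposite sides, the active change comes from one anatomical pair and the sham change from another, so their difference is not a contrast within one pair. The third session is presumably meant to address this, but neither document says how its data enter the analysis. The documents give no expected number of such children.

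6. **Whether the threshold can be recovered.** The adjusted family could be 15 tests (one contrast), 15 × 3 = 45 (all three contrasts), or 45 × 2 = 90 (both data types), and more if several frequency bands were used. Literature Review v of the protocol explains that wPLI is computed by band, but no band is fixed for the endpoint. If alpha were 0.05 and were divided by the effective number of tests (both assumptions), effective numbers from 1 to 15 would give thresholds from 0.05 to 0.05 / 15 = 0.0033. The documents do not narrow this.

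**The case against.** **The protocol's aims are broader than one pair.** This is true. Its design justification expects that rTMS "it will alter connectivity between the epileptogenic motor cortex and other connected cortices", and its purpose refers to language regions in the plural. Analysing 15 pairs is legitimate. But breadth does not settle which pair answers the objective, and the SAP neither withdraws nor replaces the named one.

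**The protocol still governs.** Also fair. The SAP's active-versus-sham Wilcoxon test, applied to the protocol pair, would be that endpoint's test if both regions are among the six. What is missing is its identification in the analysis plan.

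**Mis-coding of side is not shown.** This stands. The SAP does not say that regions have fixed labels, so the side problem is conditional.

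**The SAP is in the past tense, so changes now are after the fact.** This stands and limits the remedy. Naming the pair is not data-driven, because its priority dates from 2020. Giving it a fresh alpha allocation would be a later decision.

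Three stronger readings are tempting and unsupported:

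- *False positives are uncontrolled.* Fifteen independent unadjusted tests at 0.05 would give 1 − 0.95^15 = 0.537, but the SAP does adjust, so this is not the trial's error rate.
- *The endpoint loses a known amount of power.* With a paired t test, 36 analysed children, a standardised effect of 0.5 and two-sided 0.05, noncentral-t power is 83% at 0.05 and 45% at 0.05 / 15. Alpha, the effect size and the effective number of tests are all assumed, and the SAP uses a Wilcoxon test, so this is illustration only.
- *Another pair was promoted because the protocol pair disappointed.* Nothing in either document shows this.

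**Conclusion.** The point holds as a gap in endpoint identity and should be fixed. One named pair in the protocol becomes at most one of 15 in the SAP, with equal status, and the text cannot confirm that it is among them. This rests on the wording of the two documents and needs no numerical assumption.

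The side-coding consequence is conditional. If the regions carry fixed left/right labels, no single pair is the protocol endpoint for the whole sample; about 11 of 36 children (6 to 15 across the range tried) would fall under a different pair from the rest, on the assumptions stated. The possibility that another pair is presented as the connectivity result is open but not shown.

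**What to change.** In the SAP and the report:

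- Designate the active-versus-sham wPLI change for the protocol pair as the test that answers the connectivity objective, for each of the two data types. Code the motor region by the side actually stimulated and hold the frontal region on the left. Report it whatever the result.
- State how children whose side switched, and their third sessions, are handled in the analysis.
- Label the other pairs exploratory and keep the principal-component adjustment for them.
- Name the six regions, the frequency band or bands, the effective number of tests, the threshold and the family it covers.
- Disclose the expansion from one pair to 15.
- Give the protocol pair's unadjusted p value beside its principal-component-adjusted threshold. If a separate alpha family across the two data types is used, for example Holm, say that it was added after the SAP.

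The cost is a SAP note, any recoding of the motor region by side, and a few lines in the report; no new data are needed. The downside is that the other pairs lose any confirmatory status. The gain is an identifiable, prespecified endpoint. No power gain is claimed, because alpha, effect size and the effective number of tests are not in the documents.
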